9.4.2 ANALYSIS OF THE PRIMARY EFFICACY ENDPOINT(S)

Primary analyses of these clinical trial data will be descriptive, including critical event rates reported with 95% confidence intervals.

9.4.3 ANALYSIS OF THE SECONDARY ENDPOINT(S)

First, we will graphically plot the relationship between the secondary endpoint and dose. We will explore these plots to determine a reasonable functional form (i.e. linear, Emax, log transformed, log-logistic) for dose-response. We will consider dose as a linear predictor in addition to the most reasonable functional form. However, we will not fit other models if the linear predictor is reasonable.

We will fit generalized linear models to predict change in glucose from baseline given dose. We will use a random effects model (with a random intercept for each subject). The main predictor variable will be dose. The main covariate will be the baseline value for the covariate for variables that are measured longitudinally (i.e. model predicts 4 hour glucose, and baseline glucose is a covariate in the model).

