4 STUDY DESIGN

4.1 OVERALL DESIGN

This is a phase 1 study to determine the safety and tolerability of 100 – 1000 U regular short-acting intranasal insulin in 24 healthy adult volunteers. The primary endpoint will be severe hypoglycemia using a numerical cutpoint of blood glucose <45 mg/dL as a binary variable. The secondary endpoints will include the change in blood glucose, serum insulin, and serum C-peptide levels for up to 4 hours after drug administration to evaluate for any systemic absorption of intranasal insulin.

Experiments will be conducted at the Michigan Clinical Research Unit, which offers all the clinical research services necessary to study investigators at Michigan Medicine. Participants will be serially exposed to escalating doses of intranasal regular insulin.

Participants will be asked to participate in 6 administrations over 5 sessions with a 1-week washout interval between each session. The first session will include an initial control administration of 0 U followed by 4 hours of observation, then followed by the first dose-escalation administration and another 4 hours of observation. Subsequent visits will involve a single dose-escalation administration per visit. The starting escalation schedule will use dose increments of 200 units for a schedule over 6 administrations of 0 U, 200 U, 400 U, 600 U, 800 U, and 1000 U. Any subject experiencing a hypoglycemic episode meeting the definition of serum glucose level <45 mg/dL or having any related or possibly related serious adverse event will not be given a subsequent dose escalation.

Adaptive Design: For every 6 participants, iterations of a Bayesian model will be performed to associate the administered dose with the frequency of dose-limiting hypoglycemia or other adverse events. The model will adaptively reallocate the dose increments for the next 6 participants. To provide more precise and reproducible estimates of dose-limiting toxicity, the trial will modify the size of dose increments based on the developing model to allocate more administrations to areas of the model with greatest uncertainty, or to higher doses in the absence of dose-limiting hypoglycemia. This will provide more observations and the greatest information density at doses of greatest interest that are most relevant to the determination of maximally tolerated dose. Safety and tolerability will be assessed for approximately 4 hours after each insulin administration.

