6 STUDY INTERVENTION

6.1 STUDY INTERVENTION(S) ADMINISTRATION

Regular insulin (Humulin R U500, Eli Lilly, Indianapolis IN) at a concentration of 500 U/mL will be used to create ≤ 2 mL doses containing between 0 – 1000 U. The ≤ 2 mL doses will be administered intranasally using a 5 mL syringe divided into ≤ 1 mL per nostril. Intranasal administration will be performed with the participants supine with the neck extended (a modified Mygind position)(19, 20, 21). to mimic the position of comatose OHCA patients. Participants will be instructed to sniff following intranasal administration and rest in supine position for 15 minutes.

A total of 11 possible doses will be tested, ranging from 0 to 1000 U insulin.

Each volunteer will come for 5 study visits. In the first visit, the volunteer is administered placebo. They will receive the first assigned intranasal insulin dose 4 hours later followed by another 4 hours of observation. During visits 2-5, they will receive additional escalating doses based on the dosing protocol.

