6.1.2 DOSING AND ADMINISTRATION

Rules for assigning patients

Within subject rules (subject progressing through tiers for cohort):

1. If a volunteer experiences severe hypoglycemia (blood glucose <45 mg/dL), they will be assigned a dose 100 U less for the next round and for all subsequent rounds.
2. If a volunteer experiences severe hypoglycemia a second time, they will be withdrawn from the study.

Study wide rules (determine which dose tiers are allowable for all future volunteers):

1. All doses from 0 to 1000 U by increments of 100 U will be eligible for testing in the study.
2. If there is greater than 0.9 probability that a dose has a greater than 0.1 toxicity rate, that dose will be removed for all future cohorts (see below).

Allocation Rules

Initial Allocation and Strategy:

Overall, the philosophy of allocation is to assign as many patients as possible to higher doses, while also limiting exposure to toxic doses. The trial will start the first cohort with 200, 400, 600, 800, and 1000 U.

Allocation Adjustment Rules:

After each hypoglycemic event, we will recalculate the toxicity probabilities for that dose to see if a dose removal threshold has been met.

If a dose meets the criteria for removal, that dose and all higher doses will be removed from future participants and cohorts. For the next cohort or patient within a cohort, the highest additional doses available will be used. For example, if 700 U was removed, then 200, 300, 400, 500, 600 U would be the new future allocation.

If a cohort completes with no observed episodes of dose-limiting toxicity (DLT), the smallest (and any smaller) doses will drop, and the highest unused dose will replace it. For example, after zero episodes of DLT in Cohort 1 at any dose, Cohort 2 will use 400, 600, 800, 900, and 1000 U. Doses 100 and 200 U will be dropped.

If a cohort has any DLT, but no dose is dropped (only 1 DLT in two different doses for example), the initial allocation rules will be used for the next cohort (200, 400, 600, 800, 1000 U).

4 Cohort Example - No DLT (Demonstrated by Schema Figure 1.2.2)

Cohort 1: Participants #1 to 6

The doses will be 0, 200, 400, 600, 800, and 1000 U.

Cohort 2: Participants #7 to 12

If there were 0 events in Cohort 1, then the doses for Cohort 2 will be 0, 400, 600, 800, 900, and 1000 U. 200 U will be dropped and 900 U will be entered.

Cohort 3: Participants #13 to 18

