9 STATISTICAL CONSIDERATIONS

9.1 STATISTICAL HYPOTHESES

- Primary Efficacy Endpoint(s): Severe hypoglycemia (DLT) as defined by blood glucose <45mg/dL.

The maximum dose that is under the threshold of a 0.9 probability of having a DLT proportion of greater than 0.1 will be considered the maximum tolerated dose for this study.

- Secondary Efficacy Endpoint(s): Change in blood glucose, insulin, and C-peptide levels for up to 4 hours after drug administration to evaluate for any systemic absorption of intranasal insulin.

Our main secondary hypothesis is the secondary efficacy endpoints are not associated with increasing doses of insulin. For example, change in blood glucose from baseline to 4 hours will be similar in the placebo and highest doses.

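### The planned dose slope for the secondary endpoints mixes any dose effect with any drift across visits, because doses rise with visit and 9.4.3 names no visit term

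*Combined protocol and SAP*

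**What the plan says.** Dose order. Section 4.1 states: "Participants will be serially exposed to escalating doses of intranasal regular insulin". The control comes first: "The first session will include an initial control administration of 0 U followed by 4 hours of observation", with the first active dose later in the same session. After that, "Subsequent visits will involve a single dose-escalation administration per visit". Section 6.1 agrees: "During visits 2-5, they will receive additional escalating doses based on the dosing protocol". Section 6.3 rules out randomisation.

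Schedules. The starting plan in 4.1 is a "schedule over 6 administrations of 0 U, 200 U, 400 U, 600 U, 800 U, and 1000 U". If Cohort 1 has no DLT, 6.1.2 says "then the doses for Cohort 2 will be 0, 400, 600, 800, 900, and 1000 U"; after a second clean cohort, Cohorts 3 and 4 receive 0, 600, 700, 800, 900 and 1000 U. If a cohort has a DLT but no dose is removed, the next cohort goes back to the starting plan. A participant with severe hypoglycemia is moved down 100 U for later rounds, so the ascent can be broken.

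Model and hypothesis. Section 9.4.3 says: "We will use a random effects model (with a random intercept for each subject). The main predictor variable will be dose". It adds the baseline value as the main covariate. No visit, period or sequence term is named there or elsewhere, and no sensitivity analysis for one. Section 9.1 hypothesises that the secondary endpoints are unrelated to dose and gives as an example that "change in blood glucose from baseline to 4 hours will be similar in the placebo and highest doses".

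**The concern.** A subject-level random intercept removes stable differences between people. It does nothing about change within a person over about four weeks, and within a person dose and visit rise together. Any trend over visits in the 4-hour response is therefore credited to dose.

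This can mislead in both directions. A downward trend would look like systemic absorption of insulin. An upward trend would offset real glucose lowering and yield the absence of association that 9.1 hypothesises. Section 3 uses these endpoints to describe systemic absorption at doses above 160 U, where it says the formulation has not been characterised, so the distinction affects what the trial may claim.

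**Working it through.** **Inputs.** The schedules come from 4.1 and 6.1.2. The documents give no SD, alpha or power for this analysis. The only operating characteristics stated are those of the DLT rule in 9.2. They reproduce (0.2062 declared toxic at a true rate of 0.1) but do not bear on this point. Assumed here: two-sided 5% level, residual SD 10 mg/dL, between-person SD 5 mg/dL, linear drift per visit.

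**Layout on the no-DLT path (6 people per cohort, 144 administrations).**

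| Cohort | Visit 1, first | Visit 1, second | Visit 2 | Visit 3 | Visit 4 | Visit 5 |
|---|---|---|---|---|---|---|
| 1 | 0 | 200 | 400 | 600 | 800 | 1000 |
| 2 | 0 | 400 | 600 | 800 | 900 | 1000 |
| 3, 4 | 0 | 600 | 700 | 800 | 900 | 1000 |

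All 24 people receive 0 U only at Visit 1 and 1000 U only at Visit 5. With dose and visit both categorical, 1000 U versus 0 U is not estimable.

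**Correlation and bias.** Take dose d in units of 1000 U and visit v coded 1, 1, 2, 3, 4, 5, both centred within person.

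- S_dv = 6 × (3.000 + 2.733 + 2.333 + 2.333) = 62.4
- S_dd = 6 × (0.700 + 0.688 + 0.633 + 0.633) = 15.93
- S_vv = 24 × 13.333 = 320
- Correlation = 62.4 / √(15.93 × 320) = 0.874
- Slope shift per 1 mg/dL per visit of drift = S_dv / S_dd = 62.4 / 15.93 = 3.92 mg/dL per 1000 U within person. The random-intercept GLS fit, which also uses dose differences between cohorts, gives 3.85 (between-person SD 5) to 3.89 (SD 10).

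If all cohorts use the starting schedule: S_dv = 24 × 3.000 = 72 and S_dd = 24 × 0.700 = 16.8. The correlation is 72 / √(16.8 × 320) = 0.982 and the shift is 72 / 16.8 = 4.29.

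**Illustrative error rates, no-DLT path.** The GLS standard error (SE) of the dose-only slope is 2.48 mg/dL per 1000 U.

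- No dose effect, drift 1 mg/dL per visit: 3.85 / 2.48 = 1.55, and Φ(−1.96 + 1.55) ≈ 0.34. A simulation gave 33%. At 0.5 and 2 mg/dL per visit the rates are about 12% and 87%.
- True slope −8, no drift: 8 / 2.48 = 3.22, power about 90%.
- True slope −8, opposing drift +1: expected slope −8 + 3.85 = −4.15, power about 39% (36% by simulation).
- True slope −8, opposing drift +2: expected slope −8 + 7.70 = −0.30, power about 5%.

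**What a visit term costs.** Adding linear visit inflates the within-person variance by 1 / (1 − r²).

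- No-DLT path: inflation 4.23. The GLS SE goes from 2.48 to 4.98 (2.0 times), and with no drift power for −8 falls to about 36%.
- Starting schedule throughout: inflation 28. The SE goes from 10 / √16.8 = 2.44 to 10 / √(16.8 / 28) = 12.9 (5.3 times), and power falls to about 10%.

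**Dependence on the Visit 1 pair.** The adjusted slope is estimable partly because two doses share Visit 1, but 0 U is always first and the active dose follows about 4 hours later. By GLS on the no-DLT path, a 1 mg/dL order effect on the second administration shifts the dose-only slope by −0.24 and the visit-adjusted slope by +0.97. With an assumed 5 mg/dL order effect and no dose effect, rejection is about 8% without the visit term (5 × 0.24 / 2.48 = 0.48) and 16% with it (5 × 0.97 / 4.98 = 0.97). Adding an indicator for that second administration removes this bias. The same GLS calculation then gives an SE of 5.76 on the no-DLT path (5.76 / 2.48 = 2.3 times the dose-only SE) and 16.1 if the starting schedule is repeated (16.1 / 2.44 = 6.6 times).

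**The case against.** Four objections carry weight.

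1. **Drift is hypothetical.** The outcome is change from each administration's own baseline, with baseline as covariate, so shifts in glucose level from assay, season or eating habits largely cancel. Only drift in the 4-hour response matters, and the documents offer no evidence of it. This stands, and it is why the error rates are illustrative. The confounding itself follows from the schedule alone.
2. **The remedy is weak.** The visit-adjusted slope leans on the Visit 1 pair, loses precision badly and, with no drift, misses a real effect more often than the planned model. Making it the sole basis for a conclusion could increase the very error that is feared. This stands and limits the fix to a sensitivity role.
3. **A visit term is not excluded.** Section 9.4.3 speaks of the main predictor and main covariate, so other terms are allowed. But allowed is not prespecified, and the choice could then follow the data.
4. **Scope.** This is a secondary analysis with no stated alpha, 9.1 offers the contrast only as an example, and absorption is also judged from insulin, C-peptide and the PK/PD modelling in 9.4.4. This stands; the primary DLT rule is not affected.

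A reader might also infer that the planned model tests the joint null of no dose effect and no visit change. It does not: the slope reflects their sum, and the two can cancel. Nor is it guaranteed that every participant ascends or that the example contrast is always Visit 1 versus Visit 5. A step-down after a DLT, or a dropped dose, can break the pattern.

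**Conclusion.** The point holds in a limited form. Under the planned schedule, the dose slope in 9.4.3 is the dose effect plus a share of any visit-to-visit drift in the 4-hour response: about 3.9 mg/dL per 1000 U for each 1 mg/dL per visit on the no-DLT path, and 4.3 if the starting schedule is repeated throughout. These multipliers rest on the schedule and a linear drift; they barely depend on the SDs. The false-positive and power figures rest on assumed SDs and drift sizes. The documents do not support a claim that the analysis will give a wrong answer, or that a visit-adjusted slope would settle the matter. They do support saying that, on the no-DLT path, the example in 9.1 cannot be attributed to dose rather than visit. The ascending order itself is not in question here.

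**What to change.** **Section 9.4.3.** Keep the planned dose model. Prespecify two sensitivity fits: one adding visit number (1 to 5) as a linear covariate, and one adding both visit number and an indicator for the second Visit 1 administration. Report the dose slope from all three with 95% CIs. Do not make the visit-adjusted slope the sole decision rule.

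**Section 9.1.** State that the example contrast cannot be attributed to dose separately from visit. State also that a conclusion of association or of no association is qualified if the slopes differ materially, or if the adjusted interval is too wide to exclude a relevant effect.

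**Cost.** Two extra fits per endpoint and a few sentences; no new data and no change to dosing. The drawback is the loss of precision shown above, which may leave the adjusted fits uninformative if every cohort repeats the starting schedule. The report should say so if that happens.

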1.3 SCHEDULE OF ACTIVITIES (SOA)

Schedule of Events table						
Study Visits	Screening	1	2	3	4	5
Study Day(s)	-28	0	7+/-3	14+/-3	21+/-3	28+/-3
Provide study overview and participant responsibilities	X					
Informed consent	X					
Medical history and inclusion/exclusion criteria review	X					
Previous and concomitant medications	X	X	X	X	X	X
Physical examination	X					
Vital signs ¹	X	X	X	X	X	X
Urine pregnancy test (female subjects of child bearing potential)	X	X	X	X	X	X
Insertion of a short term intravenous catheter		X	X	X	X	X
Study drug administration ²		X	X	X	X	X
Clinical laboratory screening labs ³	X					
POC serum glucose ⁴		X	X	X	X	X
Serum C-Peptide ⁵		X	X	X	X	X
Serum Insulin ⁵		X	X	X	X	X
Adverse event reporting		X	X	X	X	X

¹ Vital signs include blood pressure, pulse rate, respiration rate, and temperature at supine position.

² Study drug will be administered intranasally.

³ Clinical laboratory screening labs include clinical comprehensive metabolic panel and CBC.

⁴ Point-of-care (POC) serum glucose glucometry will be performed at 0, 15, 30, 60, 120, 180, and 240 minutes after each intranasal insulin administration. Sample will be collected +/- 10 minutes of scheduled assessment.

⁵ Blood and plasma samples will be collected, aliquoted, and frozen at 0, 15, 30, 60, 120, 180, and 240 minutes after each intranasal insulin administration for blood insulin and C-Peptide measurements by the University of Michigan Pharmacokinetics Core. Sample will be collected +/- 10 minutes of scheduled assessment.

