2.3.3 ASSESSMENT OF POTENTIAL RISKS AND BENEFITS

Although hypoglycemia has never been demonstrated with intranasal insulin at lower dose in humans, the potential for this safety concern exists in this study. Mechanisms of insulin transport into the brain through the olfactory epithelium is more efficient than vascular absorption of regular insulin into the systemic circulation, but Kullmann et al have demonstrated small but measurable increases in serum insulin with intranasal administration and have shown these to represent dose-dependent spillage (11).

There is insufficient data to show whether this dose response is linear, and the very small changes in insulin level detected did not manifest as a measurable change in glucose (11). Of note, a minority of the 19 studies in which participants received 160 U of intranasal insulin also reported clinically insignificant but measurable decreases in serum glucose ranging from 0.2 to 0.4 mmol/L. Based on these data, we have developed an initially conservative dose escalation study that has the potential to adapt the magnitude of dose escalation with accumulating data if lower dose tiers demonstrate the same overwhelming safety signals seen in the prior data. Point-of-care (POC) serum glucometry will be performed at 0, 15, 30, 60, 120, 180, and 240 minutes after each intranasal insulin administration. Hypoglycemia as defined by a blood glucose of <45mg/dL will be treated with 50 ml of intravenous D50W and food. The subject will also be monitored until achieving two consecutive measurements of blood glucose > 70mg/dL, measured at 30 minutes apart. If blood glucose falls to ≤70 mg/dL but not <45 mg/dL, the blood glucose will be monitored every 30 minutes until it returns to >70 mg/dL.

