6.5 CONCOMITANT THERAPY

6.5.1 RESCUE MEDICINE

If a subject's blood glucose level falls <45 mg/dL, he/she will be treated with 50 ml of intravenous D50W and provided food. He/she will be monitored until achieving two consecutive measurements of blood glucose > 70mg/dL, measured at 30 minutes apart. If blood glucose falls to ≤70 mg/dL but not <45 mg/dL, the blood glucose will be monitored every 30 minutes until it returns to >70 mg/dL.

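### The secondary glucose model uses only the 4-hour value and has no rule for readings after rescue, so the dose effect on glucose is attenuated and could change sign

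*Combined protocol and SAP*

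**What the plan says.** Section 9.4.3 sets the target of the secondary analysis: "We will fit generalized linear models to predict change in glucose from baseline given dose". The model has a random intercept per participant, dose as main predictor and baseline as covariate. The time point is given in a parenthesis: "model predicts 4 hour glucose, and baseline glucose is a covariate in the model".

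Section 9.1 states the hypothesis behind it: "Our main secondary hypothesis is the secondary efficacy endpoints are not associated with increasing doses of insulin". Its example uses the same interval: "change in blood glucose from baseline to 4 hours will be similar in the placebo and highest doses".

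Glucose is sampled at 0, 15, 30, 60, 120, 180 and 240 minutes (1.3, 8.1.2), so the 4-hour value is the last scheduled reading. If glucose falls below 45 mg/dL, section 6.5.1 says that "he/she will be treated with 50 ml of intravenous D50W and provided food", with monitoring until two readings above 70 mg/dL, 30 minutes apart. Participants between 45 and 70 mg/dL are checked every 30 minutes until they are above 70; no rescue is named for them.

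The footnote on glucose sampling in section 1.3 adds: "Sample will be collected +/- 10 minutes of scheduled assessment". It makes no exception for the 0-minute sample. No section says how glucose measured after rescue enters any analysis.

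**The concern.** The section 3 objectives table says the secondary endpoints are there to detect systemic absorption and to characterise PK-PD above 160 U. A glucose fall is the pharmacodynamic sign of absorption. The stated model looks at glucose only at the end of observation, which loses information in two ways:

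- **Rescue.** A participant who drops below 45 mg/dL at, say, 60 minutes is given dextrose and food. The 240-minute reading then measures the treatment. This affects the participants who responded most, and more of them at any dose that has an effect.
- **Recovery.** A fall that resolves unaided by 240 minutes contributes a change near zero.

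The hypothesis is one of no association, so attenuation favours it. The trial could report DLTs at high doses as its primary result while its secondary glucose model shows little or no dose-related fall.

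**Working it through.** **1. The plan's nearest figure.** The plan gives no effect size, SD or power for the glucose model. It does give DLT rates, and every DLT triggers rescue. Section 9.2, scenario 5 (true DLT rate 0.10, N = 24), states a 0.2062 probability of declaring the dose toxic. An exact binomial recursion over cohorts of 6, with removal limits of 2/6, 3/12, 4/18 and 5/24 from section 7.1, gives early stop 0.1898, declared toxic 0.2062 and average N 21.1965. All three match. So a dose at which 10% are rescued stays in use with probability 1 − 0.2062 = 0.7938. The planning range of 0.01 to 0.25 makes such rates relevant.

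**2. Mean 4-hour change at one dose.** With rescue rate p, change u if not rescued and r if rescued:

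mean = (1 − p)·u + p·r

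Assume u = −5 mg/dL.
- p = 0.10, r = +40: 0.9 × (−5) + 0.1 × 40 = −0.5. With r = +60: +1.5.
- p = 0.20, r = +40: 0.8 × (−5) + 0.2 × 40 = +4.0. With r = +60: +8.0.

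The fall is cancelled when r = −(1 − p)·u/p, which is +45 at p = 0.10 and +20 at p = 0.20.

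**3. A small example.** Assume 2 of 24 fall from 90 to 40 mg/dL, read 90 to 160 at 4 hours after rescue, and the other 22 do not change.
- 4-hour mean change: 2 × (90 − 90)/24 = 0, up to 2 × (160 − 90)/24 = +5.8.
- Mean change to the lowest value: 2 × (40 − 90)/24 = −4.2.

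This shows direction only. The 95% CIs (t, 23 df) are about −10.1 to +1.8 for the nadir mean and −2.5 to +14.2 for the +5.8 case, so both include zero.

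**4. Slopes from the planned type of model.** Simulation with 4,000 participants, each given six doses from 0 to 1000 U, and a random-intercept model on dose and baseline. Assumptions, none from the documents: baseline mean 90 mg/dL, lognormal sensitivity between participants, 25% or 50% of the nadir effect left at 4 hours without rescue, and a 4-hour change of 0 to +60 mg/dL after rescue. Dose changes after a DLT were not modelled. Slopes are in mg/dL per 1000 U.

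| Nadir slope | Rescued at 1000 U | Effect left at 4 h | 4-h slope, no rescue | 4-h slope as planned, for r = 0 / +20 / +40 / +60 |
|---|---|---|---|---|
| about −10 | under 1% | 25% | about −2.5 | −2.6 / −2.5 / −2.2 / −2.1 |
| about −10 | under 1% | 50% | about −5 | −5.1 / −4.9 / −4.6 / −4.6 |
| about −20 | about 7% | 25% | about −5 | −4.2 / −3.0 / −1.5 / −0.2 |
| about −20 | 6–7% | 50% | about −10 | −8.6 / −7.0 / −6.0 / −5.0 |
| about −30 | about 19% | 25% | about −7.5 | −5.0 / −1.3 / +2.8 / +6.8 |
| about −30 | 17–20% | 50% | about −15 | −9.9 / −5.2 / −1.4 / +1.2 |

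The drop from the nadir slope to the unrescued 4-hour slope is recovery, and its size is set by assumption. The further move to the last column is rescue. In every setting, the planned slope was closer to zero than the unrescued 4-hour slope from the same run, or had reversed sign. Near 7% rescued, the slope almost vanishes only with 25% left at 4 hours and a +60 post-rescue change.

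**The case against.** **The 4-hour outcome is only illustrative.** It appears in a parenthesis and in an example, while the endpoint itself covers the whole period up to 4 hours. This is fair, but both places agree and no other time point is given for the model. An analyst following the text would fit 4-hour glucose.

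**Other evidence on absorption exists.** Insulin and C-peptide are drawn at the same seven times. Section 9.4.4 adds PK/PD modelling of serial insulin if the signal suffices, and explores glycemic variability. So 4-hour glucose is not the only evidence. None of this supplies a post-rescue rule, and the modelling is conditional.

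**Stronger readings that the documents do not support:**
- *Hypoglycemia would be missed or the MTD distorted.* Section 3 counts a reading below 45 mg/dL at any post-dose check, so a rescued low is still a DLT. Dose removal and the MTD rule use DLT counts, never the 4-hour model.
- *Every flaw favours the hypothesis of no effect.* With many rescues the slope turns positive, and that is still an association with dose.
- *A non-significant slope will be declared proof of no absorption.* Sections 9.1 and 9.4.3 state no significance rule.
- *The protocol implies an equivalence margin of 0.4 mmol/L.* Section 2.3.3 reports "clinically insignificant but measurable decreases in serum glucose ranging from 0.2 to 0.4 mmol/L" in some studies at 160 U. It does not offer this as a margin.
- *Baseline will be drawn after dosing.* The window permits a 0-minute sample up to 10 minutes late, but nothing says one is planned.

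**Conclusion.** The concern holds for the secondary glucose analysis. The stated outcome is taken after rescue or recovery for any low found before 240 minutes, and no rule deals with this. A low first seen at 240 minutes is recorded before rescue and is unaffected. For lows of 45 to 70 mg/dL the problem is insensitivity through recovery, without contamination by treatment.

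The direction is attenuation, passing through zero to a reversed sign when rescues are frequent. The size cannot be fixed from the documents. Rescue bias is slight if DLTs are rare, though recovered falls are still missed. It can cancel the slope at roughly 7% to 20% rescued at the top dose, depending on the assumed persistence and post-rescue rise. This is a moderate correction; the trial's main conclusion does not depend on it.

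**What to change.** In sections 9.1 and 9.4.3:

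1. Make the main glucose outcome the lowest post-dose value within 0–240 minutes, up to and including the last reading before any rescue, minus the pre-dose baseline. Compare it with the same participant's 0 U administration. State whether the extra 30-minute checks count; the reading that triggers rescue should count either way.
2. Add a repeated-measures model over all scheduled time points (dose by time, participant random effect) with post-rescue values excluded. Keep 4-hour change as supportive.
3. Report the top dose minus 0 U difference with a 95% CI, so that similarity is not inferred from a non-significant slope. No particular equivalence margin is required.

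In the section 1.3 sampling footnotes, state that the 0-minute sample is drawn before dosing.

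The cost is SAP wording and a footnote, as all samples are already scheduled and rescue is untouched. The downside is that a nadir is somewhat noisier than a single reading and is negative on 0 U too, which is why the 0 U comparison is needed. The outcome should be fixed before DLT data are seen, because choosing it afterwards would be post hoc.
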